## **8.2 Assessment**

### **8.2.1 Relevant Medical History**

Relevant medical history will be documented at the Screening Visit and will focus particularly on any important diseases and in case of infections or tumors, the pathogen involved or the pathological diagnosis, if available. Special attention should be given to history of prior allergic reactions, especially to vaccines.

In addition, smallpox vaccination history will be assessed (check for a smallpox vaccine scar and any documentation (written/oral) of previous smallpox vaccination, if available).

### **8.2.2 Prior and Concomitant Medications**

All concomitant (ongoing) medications except homeopathic substances and dietary supplements must be recorded in the CRF and in the subject's medical record including information about the indication, dosage regimen, and the onset and end of treatment.

The following medications, taken within three months prior to screening, will also be recorded in the CRF: Vaccines, corticosteroids (via any route of administration), other immune-modulating drugs, immunoglobulins and/or any blood products, investigational drugs and depot preparations which are still active at the date of screening.

### **8.2.3 Physical Examination**

#### Complete physical examination

A complete physical examination will be performed at the Screening Visit. The examination includes a review of major organ systems as well as height and weight. The examination should be directed at finding evidence of any infections, tumors and lymphadenopathy. In addition, auscultation of the heart and lungs to check specifically for signs of any heart condition will be performed.

#### Targeted physical examination

A targeted physical examination, guided by any signs or symptoms previously identified or any new symptoms that the subject has experienced since the last visit, is conducted at visits according to the Trial Procedure Schedule during the active trial phase. In addition, auscultation of the heart and lungs will be performed.

A grading scale for lymphadenopathy would apply as follows:

Grade 0 (normal finding): no palpable lymph nodes

Grade 1 (mild): lymph nodes up to a diameter of 1 cm, ipsilateral or bilaterally enlarged lymph nodes, signs of tenderness

Grade 2 (moderate): lymph node diameter greater than 1 cm, ipsilateral or bilaterally enlarged lymph nodes, pain, skin redness, warmth, limiting instrumental activities of daily living (ADL) (instrumental ADL refer to performing work related duties, routine physical training activities, etc.)

Grade 3 (severe): lymph node(s) diameter exceeds 2 cm, severe pain, general symptoms like fever and sweating limiting self-care activities of daily living (self-care ADL refer to performing personal needs, and not bedridden).

#### **8.2.4 Vital Signs**

Vital signs will be measured at visits according to the Trial Procedure Schedule. Blood pressure, respiration rate and pulse rate will be taken after the subject has been sitting for at least two minutes. Body temperature will be measured orally.

#### **8.2.5 Unsolicited Adverse Events**

During every trial visit following screening, the investigator has to report any unsolicited AE experienced by the subject.

All intercurrent diseases reported when the investigator actively inquiries from the subject will be documented in the source data and all required details (e.g. start and stop date, severity) will be assessed. Unsolicited AEs will be reported in the AE section of the CRF.

AEs will be assessed and documented at all visits of the active trial phase and if ongoing after the active trial phase followed until resolution or until the remote FU visit at the latest.

SAEs and AESIs will be assessed and documented at all trial visits, including the remote FU Visit. Ongoing AESIs and SAEs after first vaccination will be followed up until resolution or achievement of stable clinical conditions.

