**Trial Procedure Schedule – Group 2**

Visit (V)	SCR	V1	V2	V3	V4	V5	V6	Remote FU
Day / V +... d	-70- -1	0	V1 +6-8	V1 +13-15	V1 +27-29	V1 +41-43	V1 +55-57	Last Vaccination +182-210
Week	-10- -1	0	1	2	4	6	8	26-30
Procedures								
Informed consent	X							
Check inclusion / exclusion criteria	X	X						
Medical/Surgical History	X							
Check vaccination history and absence of vaccination scar	X							
Complete physical exam 	X							
Targeted physical exam 		X	(X)	X	X			(X)
Evaluation of vital signs	X	X	X	X	X			(X)
Recording of Baseline signs and symptoms	X	X						
Check cardiac risk factors	X							
ECG 	X			X				
Questions on cardiac signs and symptoms		X		X	X			
Review of prior/concomitant medications	X	X		X	X			(X)
Counseling 	X	X	X	X	X			
Examination of vaccination site		X	X	X	X			
Photo of vaccination site			X	X				
Bandage application / change 		X	X	X	X			
Assessment of axillary and supraclavicular lymphadenopathy		X	X	X	X			
SAE/AE/AESI recording		X	X	X	X			X 

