## **4 Trial Design**

### **4.1 Experimental Design**

This trial is a randomized, open-label Phase III non-inferiority trial to demonstrate efficacy for MVA-BN® compared to ACAM2000® in 18 to 42 year old healthy, vaccinia-naïve subjects.

#### Group 1

MVA-BN®, two standard doses s.c., 4 weeks apart followed by one dose of ACAM2000® via scarification 4 weeks after the second MVA-BN® vaccination.

#### Group 2

ACAM2000®, one dose via scarification, in accordance with US military smallpox vaccine program.

Subjects in Group 1 will participate in eleven physical trial visits, nine blood draws and one remote follow-up visit. Subjects in Group 2 will participate in seven physical trial visits, seven blood draws and one remote follow-up visit. For the schedule of the trial visits and the description of trial procedures, please refer to the trial procedure schedule and the following protocol sections.

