**4.2.3 Follow Up Phase**

**Visit 5 (Group 2: Visit 1 + 41-43 days)**

**The following tasks will be performed**

- Blood draw (serum collection) for antibody analysis (16 ml)

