**Visit 6 (Group 2: Visit 1 + 55-57 days)**

**The following tasks will be performed**

- Blood draw (serum collection) for antibody analysis (16 ml)

To monitor long-term safety, the clinical trial site will contact the subjects by remote correspondence (e.g. telephone or email) 6 months after the last trial vaccination to inquire whether SAEs and/or AESIs might have occurred since the last trial visit. In cases where a serious condition is detected, the trial subject will be asked to return for a physical examination and further work-up at the clinical trial site or (specifically in the case of deployed military subjects) at another medical unit as agreed upon by the Principal Investigator (PI).

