An adverse event (AE) with onset either on the day of a vaccination, but after the vaccination, or within the 28 days following a vaccination.

Causally Related Adverse Event:

An AE with either a ‘possible’, ‘probable’, ‘definite’, ‘unknown’ or ‘not evaluable’ or missing relationship to the vaccine.

An adverse event with missing relationship and onset before the first vaccination will not be assumed to be causally related.

Adverse Drug Reaction:

A causally related treatment emergent AE.

Serious Adverse Event:

All Serious Adverse Events (SAE) recorded with onset after the first trial vaccination and before the end of the FU phase are considered as treatment emergent regardless of the day of onset.

Adverse Events of Special Interest:

Any Adverse Event of Special Interest (AESI) which is also classified as serious will be included in the analysis of SAEs and will not be included in the analysis of AESIs. All AESIs recorded with onset after the first trial vaccination and before the end of the FU phase are considered as treatment emergent regardless of the day of onset.

Assay Cut-off Value:

The Assay Cut-off value (ACV) for the vaccinia-specific ELISA can be found in SOP BN0002809: “Automated ELISA for Detection of Vaccinia Specific Antibodies in Human Sera”, and for the vaccinia-specific PRNT can be found in SOP BN0003536: “Human Plaque Reduction Neutralization Test Using Vaccinia Virus Western Reserve”.

The Geometric Mean Titer:

The Geometric Mean Titer (GMT) is calculated by taking the antilogarithm of the mean of the \log_{10} transformed titers. Antibody titers below the ACV will be given an arbitrary value of one for the purpose of this calculation.

Seronegative and Seropositive Result:

A seronegative result is a titer below the ACV, while a seropositive result is a titer equal to or above the ACV.

Seroconversion:

Seroconversion is defined at each post baseline visit as either the appearance of antibody titers \geq ACV for initially seronegative subjects or a doubling or more of the antibody titer compared to baseline titer at Visit 1 for initially seropositive subjects. Seroconversion is not calculated if either the Visit 1 or respective post baseline visit titers are missing.

Maximum Lesion Area:

The Maximum Lesion Area (MLA) is defined as the maximum of two measurements: the lesion area measured on Day 6-8 (after scarification) or the lesion area measured on Day 13-15 (after scarification).

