3.8.3 General Considerations for AEs

MedDRA (Medical Dictionary for Regulatory Activities) version 18.0 will be used for coding of AEs.

Duration of an AE is calculated as follows:

Unsolicited AE: expressed in [days]

- end date of AE – start date of AE + 1
- in case of (partially) missing start date and/or (partially) missing end date imputed dates will be used in the calculation.
- in case the AE is ongoing at the end date, the duration will not be calculated

Solicited AEs: expressed in [days]

- end date of AE – start date of AE + 1 where end date is the last day the symptom is defined as an AE and start date is the first day symptom is defined as an AE (no matter if the AE occurred at every day between first day and last day).
- in case the AE is ongoing at the end date, the duration will not be calculated

Time interval between vaccination and start of AE are calculated as follows:

Relative day of start of AE is calculated as follows:

Unsolicited AEs: expressed in [days]

- start date of AE – date of vaccination of the corresponding period
- in case of (partially) missing start date no calculation will be done.

Solicited AEs: expressed in [days]

- start date of AE – date of vaccination of the corresponding period where start date is the first day a symptom is defined as an AE, and vaccination day corresponds to the day of vaccination for each period.

Local and General Unsolicited AEs

Any unsolicited AE which is recorded with the preferred term including the text “injection site” or “vaccination site” will be considered as a local reaction. Any other preferred terms which are

considered as local events will be documented in the DRM minutes. Any unsolicited AE not classified as a local AE will be classified as a General AE.

All available safety data collected during the FU phases will therefore be simply listed. However the new onset SAEs reported during the FU phase will be analyzed.

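### SAE and AESI recording at Group 2 Visits 5 and 6 is required by Protocol 8.2.5 but absent from the schedule, and the SAP contradicts itself on non-serious AESIs with onset in follow-up

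*Protocol*

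**What the plan says.** **Collection.** Protocol 8.2.5 requires that "SAEs and AESIs will be assessed and documented at all trial visits, including the remote FU Visit". Protocol 4.1 settles which contacts count as visits: "Subjects in Group 2 will participate in seven physical trial visits, seven blood draws and one remote follow-up visit". Seven physical visits are Screening plus Visits 1 to 6, so Visits 5 and 6 are trial visits.

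In the Group 2 Trial Procedure Schedule (Protocol 1.5), the row "SAE/AE/AESI recording" is marked at Visits 1 to 4 and at the remote follow-up, and is blank at Visits 5 and 6. SAP Table 2 shows the same pattern. Protocol 4.2.3 gives each of these two visits a single task, a serum draw for antibodies.

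Protocol 4.2.3 then has the site contact subjects six months after the last vaccination "to inquire whether SAEs and/or AESIs might have occurred since the last trial visit". The remote follow-up task list, and footnote 5 of the Group 2 schedule, tell the site to record new SAEs and AESIs without giving a start date.

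**Analysis.** SAP 3.8.3 says safety data from the follow-up phase are listed, with one exception: "the new onset SAEs reported during the FU phase will be analyzed". The SAP General Definitions say: "All AESIs recorded with onset after the first trial vaccination and before the end of the FU phase are considered as treatment emergent". They also move any serious AESI into the SAE analysis. SAP 3.10.9 reports AESIs separately but in the same manner as SAEs, and SAP 5.1 plans Table 15.3.2.2, AESI incidence on the FAS.

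**The concern.** A site cannot follow both 8.2.5 and the Group 2 schedule. If it follows the schedule, nobody asks about serious or cardiac events at two visits where the subject is present. If it then applies the remote question literally, the inquiry starts at Visit 6 and the four weeks before it are skipped.

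The occurrence of SAEs and of cardiac signs or symptoms are named secondary safety endpoints (Protocol 9.3.2), and Group 2 is the ACAM2000-alone comparator. The remote call is also not certain to happen. Protocol 4.2.3 foresees deployed subjects, and the SAP General Definitions do not count a missed remote follow-up as a protocol deviation. For a subject who misses the call, Visits 5 and 6 are the only scheduled contacts after about Day 28.

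On the analysis side, a programmer could defend either including or excluding a non-serious AESI with onset after Visit 4 (Group 2) or Visit 10 (Group 1). That choice should be fixed before database lock, not made once the events are known.

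**Working it through.** The plan states no figure on this point, so the check compares texts and uses the visit windows.

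**1. Visits without safety recording.** Group 2 has six physical visits from Visit 1 onward. Recording is scheduled at four (Visits 1 to 4) and not at two (Visits 5 and 6).

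**2. Interval at risk of not being asked about.** Windows from the Group 2 schedule: Visit 4 on Days 27–29, Visit 6 on Days 55–57, remote follow-up 182–210 days after vaccination.
- Visit 4 to Visit 6: nominally 56 − 28 = 28 days; by the windows, 55 − 29 = 26 to 57 − 27 = 30 days.
- Visit 4 to remote follow-up, the longest stretch between scheduled safety questions now: 182 − 29 = 153 to 210 − 27 = 183 days.
- Visit 6 to remote follow-up, the longest stretch if Visits 5 and 6 are used: 182 − 57 = 125 to 210 − 55 = 155 days.

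**3. Does another section resolve the collection conflict?** Protocol 8.1.3.1 ends active questioning in Group 2 at Visit 4, but it concerns AEs in general. Section 8.2.5 itself separates AEs, followed through the active phase, from SAEs and AESIs, assessed at all trial visits. So 8.1.3.1 does not override it. Section 8.2.5 also opens with "During every trial visit following screening, the investigator has to report any unsolicited AE experienced by the subject", which is broader still and conflicts with 8.1.3.1 for Group 2 after Visit 4.

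**4. Status of a non-serious AESI with onset in follow-up, by SAP section.**

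| SAP section | Treatment |
|---|---|
| 3.8.3 | Listed; the exception names SAEs only |
| General Definitions | Treatment emergent up to the end of follow-up |
| 3.10.9 | Reported like SAEs; named with SAEs as the exceptions to the rule that AEs newly reported in follow-up are listed as non-treatment emergent |
| 5.1, Table 15.3.2.2 | In an incidence table on the FAS, with no time limit in the title |
| 3.8.2 with Table 15.3.2.3 | No column: periods end at Visit 4 (Group 2) or Visit 10 (Group 1) and later onsets go to the follow-up phase |

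Section 3.8.3 conflicts with the next three rows. Serious AESIs are unaffected, because they are analysed as SAEs under either reading.

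**5. Expected yield.** The ACAM2000 prescribing information in Appendix IVc (section 5.1.3) reports 10 suspected myo-/pericarditis cases across the ACAM2000 and Dryvax recipients, with mean onset at 11 days and a range of 9 to 20. All fall inside the Day 0–28 window, which already includes ECG and troponin I at Visit 3 and cardiac questions at Visits 3 and 4.

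**The case against.** The best defence is that several safeguards sit outside the blank cells. The remote follow-up task list and footnote 5 have no start date, so an unrecorded AESI from Day 40 is still new at the call. Protocol 8.3.1 and 8.3.2 require SAEs and AESIs to be reported throughout the trial, and 8.2.7 brings in any subject with cardiac signs or symptoms for an unscheduled visit. After ACAM2000 the two groups are now followed alike: 28 days of active assessment, then one remote contact. Adding two inquiries in Group 2 alone disturbs that symmetry.

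Much of this stands. A reader might infer that nobody would ask about Days 28 to 56, but the documents support an ambiguity, not a certain gap. A reader might also infer that expedited reporting breaks down. For SAEs the 24-hour clock in 8.3.1 runs from awareness, and the AESI process is in a figure not available here, so that does not follow.

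It does not dispose of the point. Duties that begin once an event is known do not replace asking, and 8.2.5 still conflicts with the schedule. The symmetry is also only relative to ACAM2000. Counted from randomization, Group 1 has recording at every visit to Week 12 and Group 2 only to Week 4, while SAP 3.10.9 compares subjects with at least one SAE between groups by Fisher's exact test.

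**Conclusion.** The point holds as two inconsistencies that should be reconciled. First, 8.2.5 conflicts with the Group 2 schedule at two of six post-screening visits. Read literally, the remote question leaves about 28 days (26 to 30 by the windows) unasked. Second, the SAP contradicts itself on non-serious AESIs with onset in follow-up.

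A reader of SAP 3.8.3 alone might conclude that late AESIs are only listed and never counted. The General Definitions, 3.10.9 and Table 15.3.2.2 say otherwise, so the defect is a contradiction, not an established exclusion. A reader might also note that follow-up makes up (182 − 28)/182 = 85% to (210 − 28)/210 = 87% of post-dose time and take that as the share of risk left unanalysed. It is calendar time; the known onset range lies before Day 28, and the exclusion itself is not established.

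The practical effect is probably small. That judgement assumes that the onset range from 10 cases carries over to this trial, and it concerns myo-/pericarditis only; the endpoints cover any SAE and any cardiac sign or symptom. Whether sites ask at Visits 5 and 6 in practice cannot be told from the documents.

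**What to change.** 1. **Protocol schedule.** Mark SAE and AESI recording at Group 2 Visits 5 and 6 in the Protocol 1.5 schedule, the 4.2.3 task lists and SAP Table 2, so that they match 8.2.5. Align the opening sentence of 8.2.5 with 8.1.3.1 at the same time.
2. **Remote question.** In Protocol 4.2.3, ask about SAEs and AESIs since the last visit at which they were recorded. This closes the ambiguity even for a subject who misses Visit 5 or 6.
3. **SAP 3.8.3.** Extend the exception so that new-onset SAEs and AESIs in the follow-up phase are both analysed, in line with the General Definitions and 3.10.9. Show follow-up onsets separately from the Day 0–28 comparison.

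The cost is one question at two visits already attended, plus short text changes in both documents. The drawback is that Group 2 would be asked more often than Group 1 after Day 28 post-ACAM2000. Separate presentation of follow-up onsets keeps the Day 0–28 comparison unaffected.

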### Assessment of Intensity

For all unsolicited AEs not represented in the Toxicity Scale for Laboratory Values ([Appendix I; Section 17.1](#)), grading of the maximum intensity will be based on the following descriptions:

- Grade 1     An AE which is easily tolerated by the subject, causing minimal discomfort and not interfering with activities of daily living.
  
- Grade 2     An AE which is sufficiently discomforting to interfere with activities of daily living.
  
- Grade 3     An AE which prevents activities of daily living. (Such an AE would, for example, prevent attendance at work and would necessitate the administration of corrective therapy.)

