### **8.1.3 Adverse Events**

New signs, symptoms or changes in health starting after the first vaccination are documented in the AE section. AEs are recorded based on unsolicited and solicited questioning ([Section 8.1.3.1](#) and [8.1.3.2](#)).

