3.8.2 Assignment of AEs to Vaccination Period

Each AE will be assigned to a vaccination period using date and time of vaccination and date and time of start of AE. If not specified otherwise all AE tables will be presented divided into the following vaccination periods:

For Group 1:

- Vaccination Period 1 covers from Visit 1 (immediately after the first vaccination) until Visit 4 (just before the second vaccination).
- Vaccination Period 2 covers from Visit 4 (immediately after the second vaccination) until Visit 7 (just before the third vaccination).
- Vaccination Period 3 covers from Visit 7 (immediately after the third vaccination) until Visit 10.
- The Overall MVA-BN[®] Vaccination Period is the combination of Vaccination Periods 1 and 2.

For Group 2:

- Vaccination Period 1 covers from Visit 1 (immediately after the first vaccination) until Visit 4.

If start time is missing and start date of AE coincides with the date of a vaccination, the AE will be assigned to the vaccination period corresponding to the vaccination on this date.

Each AE starting at or after first vaccination not matching the definition of a solicited AE is defined as an unsolicited AE. If a solicited AE begins outside of the 15-day window following the last vaccination it will be considered an unsolicited AE regardless of the preferred term. If start time is missing and start date coincides with date of current vaccination, it will be regarded as a treatment emergent AE. If the start date is (partially) missing the AE will be regarded as a treatment emergent AE following the worst case principle. If the AE cannot be assigned to a vaccination period 1 or 2 because of a (partially) missing start date it will be assigned to the overall MVA-BN[®] vaccination period (Group 1). If the AE cannot be assigned to vaccination period 2 or 3 then it will not be assigned to a vaccination period. AEs which cannot be assigned

to a vaccination period will still be included in per subject based tables and in the listings (with partial dates).

AEs with onset after the active trial phase will be considered to fall within the FU phase.

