3.10.9 Adverse Events

Adverse Events

All AEs recorded in the screening period will be reported as baseline signs and symptoms.

A summary table will be presented of the number (and percentage) per vaccination period both per subject and for the number of events for the following events:

- Any AEs;
- Any treatment emergent AEs (i.e. onset date within 28 days after vaccination); note all SAEs are automatically considered treatment emergent regardless of onset date-
- Any Causally Related AEs (i.e. missing, unknown, not evaluable, possibly, probably, or definitely related AE); note that all local solicited AEs are automatically considered causally related;
- Any Causally related Treatment Emergent AEs;
- Treatment Emergent Severe AEs (Grade 3 or higher, for grading please refer to the CTP);
- Severe Causally related treatment emergent AEs);
- Non-serious Treatment Emergent AEs;
- SAEs;
- AESIs;
- AEs leading to discontinuation of treatment

In addition, the incidence of AEs will be calculated (i.e. the number of subjects developing a treatment emergent AE divided by the number of subjects at the time of the vaccination) with corresponding 95% Clopper-Pearson CI. The incidence of any AE will also be calculated for each vaccination period, overall and per subject.

For analysis the information will be based on the data provided from Screening Visit up until FU Visit.

All AEs will be listed by subject, including demographic information, SOC and PT.

According to the CTP no new AEs should be reported during the FU phase, except SAEs and AESIs, but if any are reported then they will be listed but considered non-treatment emergent.

The number of subjects with at least one treatment emergent AE will be compared between the groups by means of Fisher's exact test.

Serious Adverse Events

The number of subjects with at least one SAE will be compared between the groups by means of Fisher's exact test.

SAEs will be listed in the same manner as AEs.

Adverse Events of Special Interest

AESIs will be reported separately but in the same way as SAEs.

Solicited Local AEs

Solicited local AEs will be summarized by PT after each vaccination, and broken down by maximum intensity.

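### An unsolicited AE that starts after MVA-BN and worsens after ACAM2000 is tabulated at its peak grade in the MVA-BN period and not in the ACAM2000 period

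*Protocol*

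**What the plan says.** **Grading.** Protocol 8.2.5 (Assessment of Intensity) states that for unsolicited AEs outside the laboratory toxicity scale "grading of the maximum intensity will be based on the following descriptions". It describes no grade per vaccination period and no date for the maximum.

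**What is recorded.** Protocol 8.1.3: "New signs, symptoms or changes in health starting after the first vaccination are documented in the AE section".

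**Causality.** The categories in protocol 8.2.5 weigh both the appearance and the worsening of an event, in relation to MVA-BN and to the comparator.

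**Period assignment.** SAP 3.8.2: "Each AE will be assigned to a vaccination period using date and time of vaccination and date and time of start of AE". For Group 1, "Vaccination Period 2 covers from Visit 4 (immediately after the second vaccination) until Visit 7 (just before the third vaccination"), so this period closes ahead of ACAM2000. The ACAM2000 phase has a period of its own: "Vaccination Period 3 covers from Visit 7 (immediately after the third vaccination) until Visit 10". For tables that pool both MVA-BN doses, the SAP says that this "Vaccination Period is the combination of Vaccination Periods 1 and 2". AE tables are split by these periods by default.

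**Treatment emergence.** The SAP's General Definitions require an AE "with onset either on the day of a vaccination, but after the vaccination, or within the 28 days following a vaccination". There is no clause on worsening.

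**Screening-period events.** SAP 3.10.9: "All AEs recorded in the screening period will be reported as baseline signs and symptoms".

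**Tables.** SAP 3.10.9 counts treatment-emergent AEs of Grade 3 or higher, and the causally related subset, per vaccination period. Events that are not treatment-emergent are listed but not tabulated.

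**The concern.** Grade and period are taken from different moments in the event's course. The grade comes from the peak, whenever that falls, and the period comes from the start. In a one-dose trial this does no harm. Group 1, however, receives two products in sequence, and an event still running at Visit 7 can start under one and peak under the other.

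Three analyses depend on the placement:

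- The secondary safety endpoint in protocol 9.3.2 counts related Grade 3 or 4 AEs in the 28 days following each dose. An event that reaches Grade 3 after the third dose is reported under the second.
- The safety objective in protocol 3.2 compares MVA-BN, ACAM2000 alone and ACAM2000 after priming. The rule overstates severity for MVA-BN and understates it for primed ACAM2000.
- SAP 3.10.1 compares the ACAM2000 phase between groups. Group 1 enters that phase with up to eight weeks of recorded AEs. Group 2 enters with baseline signs only, so the effect is one-sided.

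Causality can also part company with the period. An investigator may rate an event related because it worsened after ACAM2000, and the SAP would then show it as a related severe event in the MVA-BN period.

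**Working it through.** The documents give no figure for how often this happens, so there is none to reproduce. The check traces the written rules on one example and then shows the size of the shift.

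**Trace.** MVA-BN on Days 0 and 28 and ACAM2000 on Day 56 (protocol synopsis). Suppose an unsolicited AE starts on Day 50 at Grade 1 and reaches Grade 3 on Day 58.

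- Period: Day 50 is after Day 28 and before Day 56, so Period 2.
- Treatment-emergent: 50 − 28 = 22 days after the second dose, within 28, so yes.
- Grade: the maximum of 1 and 3 is 3, so severe.
- Result as written: one severe treatment-emergent AE in Period 2, pooled into the overall MVA-BN period, and none in Period 3.
- Result if the worsening is a new event: Grade 1 in Period 2 and Grade 3 in Period 3.

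**An edge case.** Visit 4 falls on Days 27–29 and Visit 7 on Days 55–57, so the gap between the second and third doses is 55 − 29 = 26 to 57 − 27 = 30 days. An event starting more than 28 days after the second dose but before ACAM2000 is not treatment-emergent. It reaches only the listings, even if it worsens after ACAM2000.

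**Size per subject.** With 220 vaccinated per group, one subject is 1/220 = 0.45 percentage points. The SAP's denominator is subjects at the time of each vaccination, so 220 is the planned ceiling.

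**Illustration on assumed counts (not in the documents).** Take 2 of 220 subjects severe in Period 2 and 10 of 220 in Period 3, and add m further subjects who start in Period 2 and reach Grade 3 after ACAM2000.

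| m | Period 2 as written | Period 2 with fix | Period 3 as written | Period 3 with fix |
|---|---|---|---|---|
| 0 | 2/220 = 0.9% | 0.9% | 10/220 = 4.5% | 4.5% |
| 1 | 3/220 = 1.4% | 0.9% | 4.5% | 11/220 = 5.0% |
| 3 | 5/220 = 2.3% | 0.9% | 4.5% | 13/220 = 5.9% |
| 5 | 7/220 = 3.2% | 0.9% | 4.5% | 15/220 = 6.8% |

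The Clopper–Pearson 95% interval for 10/220 is 2.2% to 8.2%, so every corrected Period 3 value in the table lies inside it. In relative terms the Period 2 column moves more, because its assumed base is low.

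**The case against.** The strongest reply is that the plan leaves the matter open and does not decide it wrongly. Protocol 8.1.3 sends changes in health that start after the first vaccination to the AE section, and a site could read a worsening as such a change and enter it separately. That reading is possible, but the text does not settle it. It does not say that a worsening of an ongoing AE gets its own start date, that the earlier record is closed, or that the same applies after later doses. If staff read it differently, the period tables depend on who made the entry.

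The reply also narrows the point, and this part stands:

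- Solicited symptoms are collected on a fresh memory aid and summarised after each vaccination.
- SAEs and AESIs count as treatment-emergent whenever they start after the first dose. Each SAE is described individually, and AESIs are listed and tabulated separately.
- Laboratory values are summarised by visit.
- Acute illness at Visit 7 may defer ACAM2000 within the window, and an AE that the investigator considers to make it unsafe ends further vaccination. Fewer ongoing events therefore reach the third dose.
- Secondary comparisons are descriptive, and per-subject tables count the event at its peak whatever the period.

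A reader might infer three stronger things that the documents do not support:

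- That a screening-period sign which worsens can never become treatment-emergent. Protocol 8.1.2 and 8.1.3 divide entries at the first vaccination and include changes in health on both sides, so a later AE entry is not barred.
- That the analyst could not repair the placement afterwards. The CRF and its completion guide are not among the documents, and either might hold more detail.
- That the shift can be sized against the 4% of severe vaccine-related events which the appended ACAM2000 label reports in previously vaccinated recipients. That figure uses another definition of severe, and the label's AE data include diary-checklist events to be regarded as solicited, a class not affected here.

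**Conclusion.** The point holds for non-serious, non-AESI unsolicited AEs in Group 1. Read as written, the start-date rule combined with a peak grade puts worsening that occurs after ACAM2000 into the MVA-BN period and leaves it out of Period 3. The event is counted as severe only when the peak reaches Grade 3 or higher. The direction is against MVA-BN and in favour of ACAM2000 after priming.

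The size is 0.45 percentage points of severe incidence per subject with a Grade 3 or higher peak. The number of such subjects is not given and is probably small. The conclusion assumes that no CRF instruction outside these documents already makes a worsening a new event. No co-primary result is affected. The change is still worth making, because the plan's causality text and its period rule currently look at different dates.

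**What to change.** In the SAP's General Definitions, define a treatment-emergent AE as one with onset, or worsening in grade, after a vaccination. In SAP 3.8.2, assign the period by the date of that onset or worsening.

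In protocol 8.2.5, state that a grade increase of an ongoing AE or baseline sign after any vaccination is recorded as a new AE, dated at the worsening and with its own causality assessment, and that the earlier record is closed at its prior grade.

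The cost is a few sentences in each document, one CRF completion instruction and a few more AE records. Event counts rise slightly, so the tables should say that a worsening is counted as a separate event.
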